6 OFF TREATMENT AND OFF STUDY CRITERIA

Off Treatment Criteria for an Individual Subject

All patients, regardless of reason for withdrawal, will be asked to continue in the follow-up phase of the study. An individual subject may be withdrawn from the study for any of the following criteria:

- An individual subject's decision (the Investigator will attempt to determine the reason for the subject's decision).
- Non-compliance with the study medication and procedures to the extent that it is potentially harmful to the subject or to the integrity of the study data.
- Worsening of IBD symptoms as defined by a PCDAI greater than 50 or PUCAI greater than 65.
- Subjects requiring rescue treatment for IBD
- Any clinical AE, laboratory abnormality, or other medical condition or situation such that continued participation in the study would not be in the best interest of the subject (including changing medication doses due to concern for side effects).
- A change in the subject's baseline condition after enrollment, but prior to start of the treatment period so that the subject no longer meets the inclusion/exclusion criteria.
- The investigator deems a subject to be no longer fit to participate in the study.

Off Study Criteria for an Individual Subject

- Completion of study specified procedures.
- Refusal of further study follow-up by patient or legal guardian
- Lost to follow up
- Death
- Physician's discretion
- Patient withdrew from study
- Other

7 STATISTICAL CONSIDERATIONS

7.1 Statistical Analysis Plan

7.1.1. Sample size and follow up. A maximum of 6 patients will be treated in this pilot study. It is anticipated that it will require 18-24 months to accrue 6 patients. With the additional 24 months of follow up to evaluate efficacy endpoints noted in Section 2, the anticipated trial duration will be 48 months.

7.1.4. Safety Monitoring and Stopping Rules. For the purpose of safety monitoring, "toxicity" will be defined as a probable or definite regimen related severe (grade 3 or worse) adverse event occurring at any time from the start of therapy to 45 days following the last MSC administration. If we observe 1 severe (grade 3 or worse) adverse event occurring at any time from the start of therapy to 45 days following the last MSC administration in the young adult cohort we will stop the study. If we observe no attributable severe adverse events in the young adult cohort, but do observe 1 severe (grade 3 or worse) adverse events occurring at any time from the start of therapy to 45 days following the last MSC administration in the pediatric cohort, we will stop the study.

7.1.3. Future Trials. If the trial is not stopped early, then the toxicity and efficacy data will be used to plan a future trial of MSC cell therapy in pediatric patients with either CD or UC, including (i) blinded placebo-controlled phase II trials optimizing dose or administration schedule, or (ii) randomized comparison to standard therapies.

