Study Design: This study is a pilot phase 1 study of patients with moderately to severely active Crohn Disease (CD) and ulcerative colitis (UC) (≥ 18 years, Mayo score: ≥ 6 or CDAI: > 220 ; < 18 years, Pediatric Crohn's Disease Activity Index (PCDAI) > 30) or Pediatric Ulcerative Colitis Activity Index (PUCAI) > 34). [1] [2] A fixed dose will be studied: 1×10^6 cells/kg administered intravenously (IV) weekly for 4 consecutive weeks, with the option of an additional 4 weeks of treatment, at the discretion of the principal investigator. The primary outcomes are regimen-related toxicity, defined in section 5. Toxicity will be scored as a binary variable indicating occurrence or non-occurrence over a monitoring interval from the start of MSC therapy to 45 days after the last infusion. Based on the planned administration schedule of 4 weeks, the total toxicity monitoring period will have duration $28 + 45 = 73$ days. If additional weekly doses are administered, the safety assessment phase will be 45 days after the last dose given.

Three young adult patients (ages 17≤22 years) will be enrolled, staggered by at least 7 days, and monitored for toxicity over a period of 73 days. Infusions are administered over the first 28 days, followed by a 45 day monitoring period. If we observe no severe (grade 3 or worse) adverse events in the young adult cohort, we will wait a minimum of 45 days after the last MSC administration before beginning to enroll 3 more patients, ages 12≤16 (pediatric cohort). If we observe a severe (grade 3 or worse) adverse event occurring at any time from the start of therapy to 45 days following the last MSC administration in the young adult cohort we will stop the study. If we observe no severe adverse events attributable to MSCs in the young adult cohort but a severe (grade 3 or worse) adverse event occurring at any time from the start of therapy to 45 days following the last MSC administration in the pediatric cohort we will stop the study. A maximum of 6 patients will be enrolled. Assuming an accrual rate of 3-4 patients per year, it is anticipated that it will require at least 18-24 months to accrue all 6 patients.

Eligibility

This protocol allows for the treatment of both male and female pediatric and young adult patients, between the ages of 12 ≤ 22 years, with active moderate to severe CD or UC, who have failed to respond to, or are intolerant of, biologic therapy.

Inclusion criteria

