This is a pilot phase 1 treatment protocol for subjects with moderate to severe CD or UC who have failed or are intolerant of one biologic. Subjects must have had a flexible sigmoidoscopy or colonoscopy or MR enterography within 2 months of enrollment, demonstrating active inflammatory bowel disease. Subjects with moderate to severe CD are defined differently in children and adults. In patients <17 years of age, moderate to severe CD will be defined as having a Pediatric Crohn Disease Activity Index (PCDAI) score of > 30 (range 0-100) and subjects with moderate to severe UC are defined as a patients with a Pediatric Ulcerative Colitis Activity Index (PUCAI) score of >34 (range 0-85). In patients \geq 18 years of age, moderate to severe CD will be defined as a CDAI of \geq 220 (range 0-600), and moderate to severe UC defined as a Mayo score of \geq 6 (range 0-12). In our study, at the specification of the FDA IND review, a young adult cohort will be enrolled first and monitored for toxicity. A pediatric cohort will only begin to enroll if there are no serious adverse events observed in the young adult cohort. Subjects will be closely monitored both by the study team to detect and evaluate adverse events (AEs), serious adverse events (SAEs), and toxicity requiring discontinuation of the intervention.

Three young adult patients (ages $17 \leq 22$ years) will be enrolled, staggered by at least 7 days. A fixed dose will be studied: 1×10^6 cells/kg administered intravenously (IV) weekly for 4 consecutive weeks. Infusions are administered over the first 28 days, followed by a 45 day monitoring period. Our chosen dose (1×10^6 cells/kg weekly for a duration of 4 weeks) is within the dosing parameters of previous trials. In trials of MSCs in pediatric GvHD, doses as high as 8×10^6 cells/kg/dose were given up to twice per week for four weeks. [51] The rate of administration (for patients < 35 kg, total infusion over 60 minutes, and for ≥ 35 kg, 4-6 ml/minute via infusion pump) is also consistent with prior pediatric administration in patients with GvHD. [51]

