In our study, toxicity will be scored as a binary variable indicating occurrence or non-occurrence over a monitoring interval from the start of MSC therapy to 45 days after the last infusion. Based on the planned administration schedule, the total toxicity monitoring period will have duration $28 + 45 = 73$ days. If we observe no severe (grade 3 or worse) adverse events in the young adult cohort, we will wait a minimum of 45 days before beginning to enroll 3 more patients, ages $12 \leq 16$ years (pediatric cohort). If we observe a severe (grade 3 or worse) adverse event occurring at any time from the start of therapy to 45 days following the last MSC administration in the young adult cohort we will stop the study. If we observe no SAEs attributed to MSC administration in the young adult cohort but an SAE (grade 3 or worse) occurring at any time from the start of therapy to 45 days following the last MSC administration in the pediatric cohort, we will stop the study. If patients with active disease do not have >grade 2 toxicity attributed to

cells and fail to rapidly progress with disease requiring urgent therapy or surgery, and at the discretion of the principal investigator, 4 additional weekly doses may be administered. Subjects are eligible to receive up to 4 additional doses of MSCs at weekly intervals, each of which will consist of the same cell number (1×10^6 cells/kg). The safety assessment period will be 45 days from the last dose administered. A maximum of 6 patients will be enrolled. Assuming an accrual rate of 3-4 patients per year, it is anticipated that it may require at least 18- 24 months to accrue all 6 patients. With the additional 24 months of follow up to evaluate longer-term safety and efficacy endpoints, the anticipated trial duration will be about 48 months.

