If we observe no severe (grade 3 or worse) adverse events in the young adult cohort, we will wait a minimum of 45 days before beginning to enroll 3 more patients, ages 12≤16 years (pediatric cohort). If we observe a severe (grade 3 or worse) adverse event occurring at any time from the start of therapy to 45 days following the last MSC administration in the young adult cohort we will stop the study. If we observe no severe adverse events attributable to MSC administration in the young adult cohort but a

severe (grade 3 or worse) adverse event occurring at any time from the start of therapy to 45 days following the last MSC administration in the pediatric cohort we will stop the study. A maximum of 6 patients will be enrolled. Assuming an accrual rate of 3-4 patients per year, it is anticipated that it will require at least 18 – 24 months to accrue all 6 patients. With the additional 24 months of follow up to evaluate efficacy endpoints noted in Section 2, the anticipated trial duration will be about 48 months.

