5.2 SERIOUS ADVERSE EVENT

As defined by the Code of Federal Regulations (CFR), a serious adverse event (SAE) is any adverse drug experience occurring at any dose that results in any of the following outcomes:

- Death
- Life-threatening adverse event
- Inpatient hospitalization or prolongation of existing hospitalization
- Persistent or significant incapacity or substantial disruption of the ability to conduct normal life functions
- Congenital anomaly/birth defect.

An adverse event or suspected adverse reaction is considered "life-threatening" if, in the view of either the investigator or sponsor, its occurrence places the patient or subject at

immediate risk of death. It does not include an adverse event or suspected adverse reaction that, had it occurred in a more severe form, might have caused death.

Important medical events that may not result in death, be life-threatening, or require hospitalization may be considered serious when, based upon appropriate medical judgment, they may jeopardize the subject and may require medical or surgical intervention to prevent one of the outcomes listed in this definition. Examples of such medical events include allergic bronchospasm requiring intensive treatment in an emergency room or at home, blood dyscrasias or convulsions that do not result in inpatient hospitalization, or the development of drug dependency or drug abuse.

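### The stopping rule and the rule for opening the pediatric cohort conflict on attribution and on severe versus serious, so it is unclear which events trigger them

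*Protocol*

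**What the plan says.** Section 7.1.4 applies three standards in three consecutive sentences:

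- For safety monitoring, toxicity "will be defined as a probable or definite regimen related severe (grade 3 or worse) adverse event" between the first infusion and 45 days after the last.
- The young adult stop reads "If we observe 1 severe (grade 3 or worse) adverse event occurring at any time from the start of therapy to 45 days" after the last infusion, with no mention of relatedness.
- The pediatric stop begins "If we observe no attributable severe adverse events in the young adult cohort, but do observe 1 severe (grade 3 or worse) adverse events". Attribution appears in the condition on young adults but not in the pediatric trigger.

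The Synopsis (Study Design) and section 2.2 both stop on any grade 3+ event in young adults, and both open the pediatric cohort if there is none. They then introduce the pediatric stop with an attributed condition: "If we observe no severe adverse events attributable to MSCs in the young adult cohort but a severe (grade 3 or worse) adverse event" in the Synopsis and "If we observe no severe adverse events attributable to MSC administration in the young adult cohort" in section 2.2.

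Section 1.4.2 changes the other term. Its first and last paragraphs say "A pediatric cohort will only begin to enroll if there are no serious adverse events observed in the young adult cohort". In between, it uses severe (grade 3+) for the young adult stop and for opening the pediatric cohort. It then writes "If we observe no SAEs attributed to MSC administration in the young adult cohort but an SAE (grade 3 or worse") for the pediatric stop.

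The protocol treats the two terms as different. Section 5.2 makes an event serious by its outcome, including "Inpatient hospitalization or prolongation of existing hospitalization" with no reference to grade. Section 5.7 says that severe does not mean serious, and its general scale makes only grade 4 reportable as an SAE automatically.

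**The concern.** This is the only study-level rule in the protocol. One event under it ends the trial, and the absence of such events allows children to be dosed. A rule that acts on a single event must identify that event without argument.

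The disputed events are foreseeable. The guidelines in section 5.5 place infection and lymphoma under possible, and place surgery for progressive IBD, abscess and rectal bleeding under unlikely. Enrolled patients have moderate to severe disease after failure or intolerance of a biologic. If such an event reached grade 3 and was classified as those guidelines suggest, it would fall inside the literal stopping sentence and outside the 7.1.4 toxicity definition. The investigator and the Data Review Committee (DRC) could reach opposite conclusions from the same case, each citing the protocol.

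**Working it through.** **Step 1: attribution.** Take a young adult with a grade 3 event judged possible or unlikely.

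| Text | Consequence |
|---|---|
| 7.1.4, definition | Not toxicity |
| 7.1.4, Synopsis, 1.4.2 and 2.2, young adult stop | Study stops |
| 7.1.4, Synopsis and 2.2, opening clause of the pediatric stop | An unattributed young adult event appears to leave the study running |

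If the stopping sentence is literal, no trial with a severe young adult event reaches the pediatric sentence. The word attributable then does nothing there, and neither stopping sentence uses the definition. If the definition governs, both stopping sentences omit its main condition.

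Two other places do not settle it. Section 1.4.2 allows extra doses if the patient has had no toxicity above grade 2 attributed to the cells, which presupposes that a patient with an unattributed grade 3 event could still be on treatment. The Synopsis and section 2.2 refer to section 5 for the definition of regimen-related toxicity, but section 5 contains none.

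**Step 2: severe versus serious.** The two sets differ in both directions. A grade 3 event meeting no section 5.2 criterion is severe but not serious (grade 3 infusion-related allergic reactions are an exception, since section 5.6 has them reported as SAEs). A hospitalization graded below 3 is serious but not severe. The first keeps the pediatric cohort closed under the Synopsis and section 2.2 but not under the first and last paragraphs of 1.4.2; the second does the reverse.

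**Step 3: size.** The protocol states no stopping probability, so there is no figure to reproduce.

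Inputs:

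- Cohorts of 3 and 3, maximum 6 (Synopsis; 7.1.1).
- b, the chance that a patient has a grade 3+ event that is not probably or definitely related. The protocol does not give it. Assumed 5, 10, 20 and 30%, equal and independent across patients.

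Readings:

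1. Any cause, both cohorts. Stop in young adults = 1 − (1 − b)³; stop by six = 1 − (1 − b)⁶; no stop = (1 − b)⁶.
2. Attribution required in young adults only, with attributable taken to mean probable or definite (the protocol does not say so). Stop in the pediatric cohort = 1 − (1 − b)³; no stop = (1 − b)³.
3. The toxicity definition governs both cohorts. These events never stop the study.

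For b = 0.10: 0.9³ = 0.729 and 0.9⁶ = 0.531, so the stop probabilities are 27.1% and 46.9%.

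| b | Reading 1: stop in young adults | Reading 1: stop by six | Reading 1: no stop | Reading 2: stop in pediatric cohort | Reading 2: no stop | Reading 3: stop |
|---|---|---|---|---|---|---|
| 5% | 14% | 26% | 74% | 14% | 86% | 0% |
| 10% | 27% | 47% | 53% | 27% | 73% | 0% |
| 20% | 49% | 74% | 26% | 49% | 51% | 0% |
| 30% | 66% | 88% | 12% | 66% | 34% | 0% |

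The no-stop columns leave out stops caused by probable or definite events, so they are upper bounds. To include those events, suppose 20% of patients had a grade 3+ event of any cause and 2% a probable or definite one (both assumed). The chance of stopping in young adults is then 1 − 0.8³ = 48.8% on the any-cause reading against 1 − 0.98³ = 5.9% on the definition reading. By six patients it is 1 − 0.8⁶ = 73.8% against 1 − 0.98⁶ = 11.4%.

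**The case against.** The best defense is that one reading satisfies every stopping sentence: any grade 3+ event stops the study. The young adult stop appears four times, always without attribution. If no severe event has occurred, then no attributable one has, so the later clause is redundant rather than contradictory. The toxicity definition might serve only the binary toxicity outcome. This is also the reading that stops most readily, so following it would not expose children under a laxer rule.

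That reading is available, but it does not settle the matter. The definition is introduced expressly for safety monitoring, in the section on stopping rules, and this reading leaves it unused there. It gives attributable no function in three sections, and it fits poorly with the extra-dose condition in 1.4.2.

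On severe versus serious, section 7.1.4 is consistent in itself; the conflict is with 1.4.2, which lies in the background chapter. The two conditions for opening the pediatric cohort could both apply, and SAE (grade 3 or worse) may be loose shorthand. This makes the second half the weaker one. Still, no text says that the conditions are joint, and joint conditions would leave the attribution conflict untouched.

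Three smaller points stand. Section 5.5 gives guidelines to be used with clinical judgment, so an infection is not automatically possible. Every value of b is assumed, and Reading 2 also needs an assumed meaning of attributable. The figures do not quantify the severe/serious half.

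**Conclusion.** The concern holds, and the text must be corrected. The attribution conflict lies within section 7.1.4 and recurs in the Synopsis and section 2.2; the severe/serious conflict lies between those places and section 1.4.2. The protocol states this rule itself, so nothing has been deferred to a statistical analysis plan.

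The conflict follows from the text and needs no assumption. Its size does. With an assumed b of 5 to 30%, the chance that events not probably or definitely related stop the study by six patients is 26 to 88% on Reading 1, 14 to 66% on Reading 2 and zero on Reading 3. These figures illustrate how much the reading matters; they do not predict the event rate in this trial.

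**What to change.** Reconcile the Synopsis (Study Design), section 1.4.2 (all three paragraphs concerned), section 2.2 and section 7.1.4 to one trigger for stopping the study and one for opening the pediatric cohort, in identical words throughout. For each trigger, state:

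- whether attribution is required and, if so, which categories of the section 5.5 scale count, in particular possible;
- whether severity, seriousness or both apply and, if both, whether either is enough or both are needed;
- whether the same trigger holds in both cohorts;
- what happens after an event outside the trigger.

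If 7.1.4 keeps its definition of toxicity, the stopping sentences should either use that term or say that they do not depend on it. The reference to section 5 for regimen-related toxicity should point to wherever the definition stands. The choice of trigger is a clinical decision for the sponsor with the DRC, and none is proposed here.

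The cost is a wording amendment, with no extra patients, visits or procedures. Because section 1.4.2 says the young-adult-first order was specified in the FDA's IND review, the sponsor should check whether the reconciled wording has to go back to the agency.

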8 RECORDS TO BE KEPT

The CETI Research Office will maintain a password protected, restricted access database documenting the dates and doses of therapy as well as clinical chemistries and hematologic parameters. The clinical status and occurrence of any adverse events and subsequent interventions are to be kept on all patients.

- Imaging reports
- Surgical summaries
- Autopsy summaries, where appropriate

- Informed consent documents

All required clinical evaluation records will be the responsibility of Principal Investigator who will also be responsible for analysis of the clinical outcome and toxicity. The laboratory evaluation of immunological efficacy will be the responsibility of Principal Investigator.

8.1 Data Handling and Record Keeping

8.1.1 Data Management Responsibilities

The Investigator is responsible for assuring that the data collected are complete, accurate, and recorded in a timely manner. Source documentation (the point of initial recording of information) should support the data collected in the electronic data system and must be signed and dated by the person recording and/or reviewing the data. All data should be reviewed by the Investigator and signed as required with electronic signature.

8.1.2 Data Capture Methods

Data Collection: The OpenClinica database, a 21CFR11.10 compliant database, will be used for data capture. Access to the system will be limited to the study members only. The OpenClinica database will be used to capture data as per the protocol required assessments (see Table 4.2.2).

All required clinical evaluation records will be the responsibility of principal Investigator who will also be responsible for analysis of the clinical outcome and toxicity. The laboratory evaluation of immunological efficacy will be the responsibility of Principal Investigator.

8.1.3 Types of Data

Source documents include, but are not limited to, the subject's medical records, laboratory reports, ECG tracings, biopsy reports, clinic notes, pharmacy records, and any other similar reports or records of procedures performed during the subject's participation in the study.

8.1.4 Source Documents and Access to Source Data/Documents

Source documents include all recordings of observations or notations of clinical activities, and all reports and records necessary for the evaluation and reconstruction of the clinical trial. Data will be collected directly from subjects during study visits and telephone calls, or will be abstracted from the subjects' medical records. The subject's medical record must record his/her participation in the clinical trial and study treatment

(with doses and frequency) or other medical interventions or treatments administered, as well as any AEs experienced during the trial.

